#### **CHANGES DUE TO COVID-19 PANDEMIC, 3.17.2020:**

To allow for the provision of mailed supplements during the coronavirus-19 pandemic and alterations to our in person data collection methods. This is an effort to reduce subject and researcher contact while maintaining study integrity for those already enrolled.

1) Supplement refills: Supplement refills will be mailed. Subjects are being informed by phone regarding the change in procedure. UIC Investigational Drug Service will continue to dispense the supplements. UIC IDS will provide a labeled study bottle that fits with the Smart Caps being used to monitor adherence (already at home with the participant) and generic capped study bottles containing the newly dispensed supplements (probiotic/placebo or supplement). The supplements will be mailed using an overnight courier (e.g., UPS). When the pills are received, study staff will instruct over the phone/FaceTime how to refill their supplement bottles as

well as conduct a hand pill count. Subjects will be asked to save their remaining pills in the generic pill bottles provided and to return to the research staff at a later date.

2) Surveys. All surveys will be conducted by phone or via a RECap link (subject preference) that coincide with study and pill refill visits.

3) Blood draws. Subjects will be sent labeled blood tubes to have their blood drawn at their 24-28 week and third trimester clinically indicated blood draw at UIC Clinical Phlebotomy. Subjects will then bring their blood samples to a locked specimen box located outside of the UIC CRC. The subject will alert the study staff and blood tubes will be picked up by the PI processed and stored or sent to Quest Diagnostics.

4) Anthropometrics. Gestational weight at a date the coincides with our defined study visits (24-28 weeks, & 34-36 weeks) will be obtained from the EHR vs. physically measured.

5) Labor and delivery samples. Nurse mid-wives ([name] and [name]) working clinically at the time of admittance for delivery, will assist with obtaining maternal blood and venous cord blood. The PI will be alerted by phone call or text message and will retrieve the samples for processing.

**IX. Rectal swabs processing and analyses.** All maternal rectal swabs will be processed at [name] 3060/3028 COMRB lab space and stored at  $-80^{\circ}\text{C}$  until analysis. Bacterial DNA will be extracted from the rectal swab using a commercial kit following standard procedures. The microbial community will be assessed via 16s rRNA analysis, whole genome shotgun sequencing, and qPCR.

**X. Placenta analysis.** Placenta will be used to assess gene expression of iron regulatory, inflammatory proteins, and tissue iron content. Placenta will be weighed, measured, and systematically biopsied and frozen at  $-80\text{C}$  for gene and protein analysis.

*i. Nucleic acid extraction: total RNA will be extracted from homogenized placental samples by the UIC DNA services lab and shipped to UCLA for the gene expression analyses.*

*ii. Gene (mRNA) expression: 8 representative biopsy samples will be taken, with the fetal and maternal membranes removed for later mRNA expression analyses (qPCR). The samples will be placed in RNA later and stored at  $-80\text{C}$  until analyses.*

**XI. Hair analysis.** Exposure to chronic stress will be assessed by measuring cortisol from a small hair sample (70-100 strands) using a commercial ELISA kit (Alpco Diagnostics, Salem, NH). Hair cortisol has been validated against 24-hour urine cortisol as a relevant biomarker of long-term cortisol exposure.

## **XII. Data management.**

Research staff will enter all data directly into a Research Electronic Data Capture (RedCap) (Vanderbilt University, Nashville, TN) data structure. Standard checks for outliers, duplicates, and other errors associated with data entry will be conducted. Dietary data will be collected using the online Diet History Questionnaire-II (NCI, Bethesda, MD).

**XIII. Statistical analysis.** Statistical analysis will be performed using SAS (v. 9.4., Cary, NC). Variables not normally distributed will be transformed and if normality not achieved, non-parametric tests will be utilized. Data that are left censored due to undetectable levels will be analyzed using imputation or tobit regression to avoid biased estimates. Descriptive statistics including means, medians and standard deviations for continuous variables and frequency for categorical variables will be used to describe the women, serum, and rectal swabs outcomes at baseline. Differences between treatment groups (Lp299v + standard PNVI vs. standard PNVI + placebo) for the baseline variables will be compared by t-test or non-parametric equivalent with Bonferroni correction and categorical data via chi-square or Fisher exact test. The correlation between the continuous variables at each time-point, baseline, 20 – 24, 34 – 36 and delivery overall and within each group will be assessed by Spearman or Pearson correlation coefficients. A two-way analysis of variance, using a general linear model for repeated measures between treatment groups and time-points will be examined. If significant effects are observed over time, single different pregnancy time-points (i.e., 24 - 28, 34 - 36 gestational week) will be tested. All *P* values were based on a two-sided test of statistical significance accepted at the level of  $P < 0.05$ .

The rectal swabs microbial 16s rRNA sequencing data will be analyzed with QIIME and PICRUSt. Baseline microbial abundance, diversity, and predicted microbial metabolisms will be assessed. For feasibility, # of charts screened, prescreening eligible, approached, and enrolled will be calculated. The # of visits completed at each time point and end of study attrition will be determined and differences between groups calculated. Adherence (# of pills consumed) and # of SAEs/AEs will be calculated and compared between groups. Maternal stress response, maternal iron-related parameters, and inflammation at baseline, 24-28 weeks, 34-36 weeks and labor and delivery, will be evaluated using repeated measures ANOVA and ANCOVA to adjust for baseline differences. Infant iron status at delivery will be compared between groups (Student's t-test). Microbial abundance, diversity and microbial metabolisms will be compared between groups at baseline, 24-28 weeks, 34-36 weeks (Student's t-test/Mann Whitney U) and within group changes at 24-28 weeks and 34-36 weeks will be determined. The mediating effects of maternal rectal swabs microbiome, systemic inflammation and iron regulatory responses on the relationship between Lp299v on maternal stress- and iron-related outcomes will be explored using generalized linear models. Multiple comparisons and false discovery rate adjustments will be used accordingly.

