**Specific Aim 1:** To determine the impact of consuming daily Lp299v + standard PNVI vs. standard PNVI + placebo beginning between 15-20 weeks gestation through delivery on maternal iron status and metabolism. To fully characterize maternal iron metabolism and regulators of maternal iron metabolism we will measure several blood-based markers including hemoglobin, hematocrit, ferritin, transferrin receptor, transferrin saturation, serum iron, erythropoietin, systemic inflammation and hepcidin at baseline, 24-28 and 34 - 36 weeks gestation, and at

delivery. *Hypothesis: Women consuming Lp229v will have superior iron status at –24-28 and 34 - 36 weeks gestation and at delivery compared to control women.*

**Specific Aim 2:** To determine colonization and propagation of the gut microbial community with Lp299v from rectal swabs collected at baseline, 24-28 weeks and 34 - 36 weeks gestation in women consuming Lp299v + standard PNVI vs. standard PNVI + placebo. *Hypothesis: Women consuming LP299v will have greater colonization and propagation of Lp299v in their rectal swabs at –24-28 week and 34 - 36 weeks gestation compared to women consuming PNVI + placebo.*

**Specific Aim 3:** To explore the effect of daily oral Lp299v vs. placebo on infant iron status at delivery. Infant iron status will be measured (via cord blood at delivery) (i.e., hemoglobin, ferritin, transferrin, serum iron, and transferrin receptor). *Hypothesis: Infant of women consuming LP299v will have higher iron status at delivery.*

**Specific Aim 4:** To determine the feasibility and tolerability of daily oral Lp299v supplementation (15-20 weeks gestation-delivery). *Hypothesis: Feasibility and tolerability will be high in both treatment groups of the study for the duration of the trial.*

**Exploratory Aim 1:** There is some evidence that probiotic use can positively influence maternal health outcomes including mood. We will explore differences in the development of gestational hypertension, pre-eclampsia, and gestational diabetes using data extracted from the electronic health record (EHR). We will also examine changes to maternal stress response (i.e., serum 17-hydroxycorticosterone and hair cortisol via immunoassay) and self-reported stress, depression, anxiety, resilience, experiences of discrimination, childhood trauma, social support, post-traumatic stress, and spirituality via surveys in women consuming Lp299v + standard PNVI vs. standard PNVI + placebo.

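### The Aim 1 visit-by-visit tests are conditional on an effect over time rather than on Lp299v versus placebo, and the list of visits omits delivery

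*Combined protocol and SAP*

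**What the plan says.** The Aim 1 hypothesis (section 1, Specific Aim 1) is between-group and names three visits: "Women consuming Lp229v will have superior iron status at –24-28 and 34 - 36 weeks gestation and at delivery compared to control women".

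Section XIII (Statistical analysis) describes the analysis of the maternal markers twice.

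- First paragraph: "A two-way analysis of variance, using a general linear model for repeated measures between treatment groups and time-points will be examined". The next sentence sets the condition: "If significant effects are observed over time, single different pregnancy time-points (i.e., 24 - 28, 34 - 36 gestational week) will be tested".
- Second paragraph: maternal iron parameters "at baseline, 24-28 weeks, 34-36 weeks and labor and delivery, will be evaluated using repeated measures ANOVA and ANCOVA to adjust for baseline differences". No condition is attached. The paragraph ends with a general provision: "Multiple comparisons and false discovery rate adjustments will be used accordingly".

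Neither paragraph says which term or contrast decides Aim 1. The candidates are the group effect, the group-by-time interaction and a baseline-adjusted difference. Maternal blood for research is requested at labor and delivery (section VI, Labor and delivery).

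**The concern.** A preliminary test protects a later comparison only if it tests the same hypothesis. A change over gestation that is common to both arms says nothing about Lp299v, yet on the literal wording it opens the visit tests. Conversely, if placebo falls and Lp299v rises, the time effect averaged over arms can be near zero, and the tests stay shut when treatment works.

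Whichever way the condition is read, the list of visits is introduced as a definition and stops at 34-36 weeks. No visit-specific comparison at delivery is therefore stated, although the hypothesis names delivery and the sample is drawn. At stake is the visit-by-visit answer that Aim 1 asks for and, because no deciding term is named, freedom to choose among several eligible results after seeing them.

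**Working it through.** **Comparing the places**

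| Visit | Aim 1 hypothesis | Conditional single-visit tests | ANOVA/ANCOVA, second paragraph of XIII |
|---|---|---|---|
| 24-28 weeks | yes | yes | yes |
| 34-36 weeks | yes | yes | yes |
| Delivery | yes | **no** | yes |

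**Inputs.** From the documents: 40 women, four time-points, two-sided 0.05. The plan gives no power figure to reproduce. Assumed: 1:1 allocation (n = 20 per arm; the ratio is not stated), SD 1, equal correlation rho of 0.5 to 0.7 between visits, complete data, two-sample visit tests, no multiplicity adjustment.

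**Probability that the condition is met, literal reading.** For the repeated-measures ANOVA, the time effect has an F test with 3 and (40 − 2) × 3 = 114 df and noncentrality

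λ(time) = 40 × Σ(m_j − m̄)² / (1 − rho),

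where m_j is the mean over both arms at time-point j. For group-by-time, replace m_j by half the between-arm difference at time-point j.

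1. *No effect, both arms at 0, −0.5, −0.8, −0.8 SD.* m̄ = −0.525 and the sum of squares is 0.4275. λ = 34.2 (rho 0.5) or 57.0 (rho 0.7), so the condition is met in about 100% of trials.
2. *Constant 0.7 SD effect, placebo falls 0.2 SD.* The post-baseline mean is 0.35 − 0.20 = 0.15, and the sum is 0.75 × 0.15² = 0.0169. λ = 1.35 or 2.25, so it is met in 14% or 21%.
3. *Constant 0.7 SD effect, placebo falls 0.5/0.8/0.8 SD.* The means are 0, −0.15, −0.45, −0.45, and the sum is 0.1519. λ = 12.15 or 20.25, so it is met in 83% or 97%.
4. *Group-by-time, constant 0.7 SD effect, any common trend.* The sum is 0.75 × 0.35² = 0.0919. λ = 7.35 or 12.25, giving power of 60% or 83%.

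The common trend thus moves the literal condition widely and leaves the treatment-related term unchanged.

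**What follows once the tests open**

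- In scenario 1 the condition screens out almost nothing. Two independent visit tests would give 1 − 0.95² = 9.75% per marker. Simulation with the correlation included gives 8-9%.
- If the condition is read as group-by-time, the corresponding null rate is 1.0-1.5%.
- With a 0.7 SD effect at delivery only and no common trend, simulation finds the condition met and a listed visit significant in 6-7% of trials. Those are chance findings, because neither listed visit carries an effect.

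**The case against.** The sentence follows directly on a model for treatment groups and time-points, so effects over time can reasonably mean treatment effects over time. That reading is plausible and it controls error. All the unfavorable figures above need the literal one. This stands as a limit on size. It does not remove the need to say which reading applies, and it does not restore delivery.

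A reader might infer that the whole Aim 1 treatment comparison hinges on a gestational trend, or that delivery is never analyzed. The documents do not support either. The second paragraph of section XIII puts labor and delivery into an ANOVA and a baseline-adjusted ANCOVA with no precondition, and the group and group-by-time terms of the first-paragraph model are produced regardless. Only the visit breakdown is conditional.

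A reader might also take 8-9% as the trial's false positive rate. It is a per-marker figure before the multiplicity provision in section XIII. That provision is general and names no family of tests, but it cannot be ignored.

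The low opening rates depend on a placebo decline that nearly offsets the assumed benefit. A steeper decline gives 83-97%.

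Keeping baseline in a group-by-time test is not an error either, since it tests differential change from baseline, which is valid under randomization.

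**Conclusion.** The point holds for the visit-by-visit analysis of Aim 1. As written, the rule can be satisfied by something other than a treatment effect, and under either reading it omits a visit that the hypothesis names. The two descriptions in section XIII also leave the deciding comparison open.

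The mismatch in the text is certain. Its size is not, because it rests on assumed trends, effects and correlations and on the literal reading. Under those assumptions the condition ranges from nearly always met with no effect to met in 14-21% of trials with a real one. The plan should be corrected, but its ungated overall analyses remain usable.

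**What to change.** In the first paragraph of section XIII, replace the conditional sentence with:

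> For each Aim 1 marker, the Lp299v-versus-placebo comparison adjusted for the marker's baseline value (the ANCOVA described below), and not the time effect, decides Aim 1. Between-group differences at 24-28 weeks, 34-36 weeks and delivery will be reported with 95% confidence intervals, with Holm adjustment across the three visits.

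Before unblinding, the sponsor should name one deciding contrast per marker and apply the plan's false discovery rate adjustment across markers to that one P value. Two candidates fit: the joint test of the three visit differences, or their average. The choice is a trade-off for the sponsor and depends on the effect pattern expected. Under the same assumptions, before adjustment across markers, a constant 0.7 SD effect gives power of 0.77-0.89 for the joint test and 0.91-0.97 for the average. An effect at delivery only gives 0.58-0.81 and 0.20-0.25. The joint test is also non-directional, so the direction of the differences must be read from the estimates.

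The Holm step is needed. With an effect at delivery only, unadjusted visit tests after a significant joint test give 8-9% false positives at the two earlier visits, against about 4% with Holm.

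Cost: wording, and some power at individual visits, since the smallest of the three P values is held to 0.05/3 = 0.0167. No new data or patients are needed, because delivery blood is already collected. The change does not settle which marker leads.

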## 2. Methods.

- I. **Research participants.** We will recruit and enroll 40 women early in pregnancy (< 20 weeks gestation) from the University of Illinois at Chicago (UIC) Obstetrics (OB) clinics located at the University of Illinois Hospital and Health Sciences System (UIHHSS) Outpatient Care Center, Center for Women’s Health. Women will be between the ages of 18 – 45 years old and at risk for maternal ID based on hemoglobin of 10.0 – 11.9 g/dl assessed as part of standard clinical care during the first prenatal OB visit.
- II. **Eligibility, recruitment, and informed consent:** After obtaining a waiver of consent for recruitment purposes, we will complete a pre-screen eligibility checklist of women < 20 weeks gestation who are seeking prenatal care at the UIC Obstetrics Clinics at the UIHHSS Center for Women’s Health. Potentially eligible women will be identified through clinic schedules and eligibility assessed via Cerner/EHR (only if data is available, data will not be available for new UIC patients). Women identified as potentially eligible through the EHR data or new UIC patients attending their first OB prenatal appointment will be approached in clinic. A research team member will introduce the study, assess interest, and further determine eligibility using a screening checklist. Interested and eligible women will be asked to provide contact information. As part of routine care, maternal hemoglobin will be assessed following the first OB visit. For women that express interest in the study and provide contact information, hemoglobin results will be followed up in Cerner. Women will be called regardless of their results to report on continued study eligibility. If hemoglobin is within the study defined range (10.0 – 11.9 g/dl) women will be invited to participate. Those who continue to express interest will be asked to schedule a baseline appointment at the UIC Clinical Research Center (CRC)s. Women will be consented at the baseline visit. Research personnel will explain to every eligible woman that their choice to participate will in no way affect their standard of care at UIHHS.

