### III. Inclusion/exclusion criteria.

- a. Inclusion criteria: obtaining prenatal care at UIC; initial prenatal hemoglobin between 10.0 – 11.9 g/dl; 18 - 45 years of age; spontaneous/natural conception; singleton pregnancy; < 20 weeks gestation; and willing to: a) fast for at least 2 hours prior to research data collection visits (3 occasions), b) agree to randomization; c) ingest Lp299v + standard PNVI or standard PNVI + placebo daily through delivery; c) refrain from **ALL** other supplements including other PNVs unless medically indicated (e.g., folate); d) attend 3 research data collection visits at UIC; e) undergo 3 venipunctures; and f) come to UIC on 4-5 occasions (separate from research visit but will be coordinated around standard clinical care visits) to pick up supplements and have study compliance monitored/checked. Women will also be able to read and write English, and have access to a smart phone. Also, women must agree to refrain from **ALL** other pre and probiotic supplements (unless medically indicated) including Activia yogurt, Kefir, Tropicana Probiotic, and Good Belly products while in the study.
- b. Exclusion criteria: Autoimmune disorder; current or previous premature rupture of membranes or clinical chorioamnionitis; current bacterial or viral infection; oral antibiotic use in the last 3 months; receiving steroid or anti-inflammatory treatment; previous bariatric surgery; malabsorptive condition; current hyperemesis; hematologic disorder (i.e., sickle cell disease or hemochromatosis); current tobacco use or within the past 1 month; current alcohol consumption; current drug use; or type 1 or 2 diabetes given these factors may influence the biological markers.

**IV. Randomization.** Women will be randomized to the Lp229V + standard PNVI or standard PNVI + placebo following the baseline visit.

**V. Treatment groups.** Women will be assigned to one of two treatment groups as described below.

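### Cord-blood iron markers are compared by an unadjusted t-test; adding one maternal baseline marker as a covariate is a cheap improvement whose gain depends on a correlation the documents do not give

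*Combined protocol and SAP*

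**What the plan says.** Specific Aim 3 is "To explore the effect of daily oral Lp299v vs. placebo on infant iron status at delivery". It lists cord hemoglobin, ferritin, transferrin, serum iron and transferrin receptor, and hypothesises higher iron status in the probiotic arm. Section XIII (Statistical analysis) gives the whole analysis in one sentence, "Infant iron status at delivery will be compared between groups", by Student's t-test, with no covariate. The sentence before it covers maternal stress, iron and inflammation outcomes, which "will be evaluated using repeated measures ANOVA and ANCOVA to adjust for baseline differences". That adjustment is not extended to the infant.

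Specific Aim 1 measures in the mother "hemoglobin, hematocrit, ferritin, transferrin receptor, transferrin saturation, serum iron, erythropoietin, systemic inflammation and hepcidin at baseline". Section IV (Randomization) places allocation after that visit: "Women will be randomized to the Lp229V + standard PNVI or standard PNVI + placebo following the baseline visit". Section VIII (Blood processing and analyses) lists the same method for maternal and cord samples for hemoglobin, serum iron, ferritin, soluble transferrin receptor and hepcidin. It lists no assay for transferrin itself.

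**The concern.** A covariate fixed before randomisation and related to the outcome reduces the residual variance of a treatment comparison and introduces no bias from treatment. Such covariates are already being collected here, and the plan accepts the principle for the mothers. With about 20 infants per arm at most, and no stratification on iron status described, the arms can differ by chance in maternal iron. The t-test allows for that in its error rate but does not correct the particular estimate obtained.

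At stake is the width of the interval for Aim 3. There is also a reporting risk: if baseline testing shows a maternal imbalance, the plan gives no rule for what to do about the infant result. That leaves the choice between adjusted and unadjusted analyses until after the data are seen.

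**Working it through.** **Inputs from the documents.** Planned enrolment: "We will recruit and enroll 40 women early in pregnancy". Two-sided 0.05 significance (Section XIII). Withdrawal of at most 15% is a feasibility criterion, not a sample-size assumption; it leaves 40 × 0.85 = 34 women.

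**Assumptions.** The documents give no allocation ratio, power, effect size, SD or maternal-cord correlation. I assume 1:1 allocation (n = 20 per arm, or 17 after 15% withdrawal), 80% power, differences in SD units, and a within-arm correlation ρ between the maternal baseline marker and the cord marker, varied from 0 to 0.5. There is no design figure in the plan to reproduce, because 40 is stated without a derivation.

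**Unadjusted t-test.** The normal approximation gives (1.960 + 0.842) × √(2/n): 2.802 × √(2/20) = 0.886 SD and 2.802 × √(2/17) = 0.961 SD. The exact noncentral t with 2n − 2 degrees of freedom gives 0.909 and 0.991 SD, which I use below.

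**Adding one covariate.** The variance is multiplied by (1 − ρ²) × (1 + 1/(2n − 4)), with 2n − 3 degrees of freedom. Examples: n = 20, ρ = 0.5 gives 0.75 × 37/36 = 0.771; n = 17, ρ = 0.3 gives 0.91 × 31/30 = 0.940.

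| ρ (assumed) | Variance ratio, n = 20 | Detectable difference, n = 20 (t-test 0.909) | Variance ratio, n = 17 | Detectable difference, n = 17 (t-test 0.991) |
|---|---|---|---|---|
| 0 | 1.028 | 0.922 | 1.033 | 1.008 |
| 0.1 | 1.017 | 0.918 | 1.023 | 1.003 |
| 0.2 | 0.987 | 0.904 | 0.992 | 0.988 |
| 0.3 | 0.935 | 0.880 | 0.940 | 0.962 |
| 0.4 | 0.863 | 0.845 | 0.868 | 0.924 |
| 0.5 | 0.771 | 0.799 | 0.775 | 0.873 |

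**Break-even.** The detectable difference is unchanged at ρ of about 0.17 for 20 per arm and 0.19 for 17. With fewer cord samples it rises, to about 0.23 at 12 per arm and 0.26 at 10.

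**Gain against loss.** For ρ of 0.3 to 0.5 the gain is 0.03 to 0.11 SD at 20 per arm and 0.03 to 0.12 SD at 17. The worst case, ρ = 0, costs 0.922 − 0.909 = 0.013 SD or 1.008 − 0.991 = 0.017 SD.

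**Power.** For an illustrative true difference of 0.8 SD at 17 per arm, power is 61.9% by t-test. With the covariate it is 60.8%, 64.4%, 67.9% and 72.8% at ρ = 0.1, 0.3, 0.4 and 0.5.

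**Chance imbalance.** The standard error of a baseline difference is √(2/20) = 0.32 SD, so an imbalance above 0.5 SD in either direction occurs with probability P(|Z| > 1.58), about 11%. At 17 per arm it is √(2/17) = 0.34 SD and about 15%. If ρ were 0.5, a 0.5 SD imbalance would move the unadjusted cord difference by 0.5 × 0.5 = 0.25 SD.

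**The case against.** Under randomisation the t-test is unbiased and holds its error rate. The aim is worded as exploratory, the work is described as a pilot, and 40 carries no power claim. All of that stands, and it makes this an efficiency point. It does not remove the point: Aim 3 is a numbered Specific Aim with a directional hypothesis, listed apart from the two Exploratory Aims.

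The contrast with the maternal analysis is also looser than it first appears. ANCOVA there adjusts a marker for its own earlier value in the same woman. A cord marker has no baseline, so using the mother's value is a further modelling choice and its absence is not a plain inconsistency.

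Three stronger readings are tempting, and the documents do not support them.

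- *That the adjustment is free.* It costs a degree of freedom and loses slightly below the break-even correlation. The Background links maternal stress to lower infant iron at birth and expects that reducing stress could help both mother and infant. It does not say that an early-pregnancy maternal marker predicts the matching cord marker. Hemoglobin may be a weak covariate because entry is limited to 10.0-11.9 g/dl; ferritin and transferrin receptor are not directly restricted.
- *That the infant comparison is the smallest in the trial.* No number of cord samples is given. Rectal swabs and hair are optional, maternal delivery blood faces the same losses by delivery, and placental blood is the fallback when cord blood is banked.
- *That every cord marker has its own maternal counterpart.* Cord transferrin does not: no transferrin assay is listed, and the maternal markers are transferrin receptor and saturation.

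**Conclusion.** The point holds as a minor, low-cost improvement. The planned analysis is valid, but it leaves unused a pre-randomisation covariate that is already collected. The likely benefit ranges from nothing at a correlation near 0.2 to a fall in detectable difference of about 0.1 SD at 0.5, with a maximum loss of 0.01 to 0.02 SD at 17 to 20 per arm. These sizes rest on assumed 1:1 allocation, 80% power and an assumed correlation; none of the three is in the documents. Removing the effect of chance imbalance in the chosen marker, and fixing the model in advance, are modest further reasons to make the change. Even at a correlation of 0.5 the detectable difference stays near 0.8 SD, so adjustment does not make Aim 3 well powered.

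**What to change.** Before unblinding, replace the t-test sentence in Section XIII with the following rule.

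- For each cord marker, fit a linear model with treatment arm and one pre-named maternal baseline marker. Use the same marker where it is measured in the mother, and otherwise log ferritin (for example for cord transferrin).
- Transform outcome and covariate where skewed. The section's existing provision for left-censored values can stay, since tobit regression also takes a covariate.
- Report the adjusted difference, or the geometric mean ratio for logged markers, with a 95% CI.
- Keep the unadjusted t-test as a sensitivity analysis.
- Use one covariate only, given 34 to 40 infants, and none measured after randomisation. Gestational age at delivery therefore stays out of the main model.

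The cost is a sentence or two of text and one degree of freedom per model. No new samples or assays are needed for the covariate.
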